10.8.5. Efficacy Tables

Efficacy: Tables							
No.	Population	IDSL / Example Shell	Title	Programming Notes	Deliverable [Priority]		
L/M ratio	L/M ratio						
2.1.	Evaluable	EFF_T1	Summary of Absolute L/M Ratio Values	Summary by: Study group and Visit Page by: Timepoint	SAC		
2.2.	Evaluable	EFF_T1	Summary of Change in L/M Ratio Values	Note: CFB, Summary by: Study group and Visit, Page by: Timepoint	SAC		
2.3.	Evaluable	EFF_T1	Summary of %Change in L/M Ratio Values	Note: %CFB, Summary by: Study group and Visit, Page by: Timepoint	SAC		
Fraction	Fractional excretion of sucralose						
2.4.	Evaluable	EFF_T1	Summary of Fractional Excretion of Sucralose Values	Summary by: Study group and Visit, Page by: Timepoint	SAC		
2.5.	Evaluable	EFF_T1	Summary of Change in Fractional Excretion of Sucralose Values	Note: CFB, Summary by: Study group and Visit, Page by: Timepoint	SAC		
2.6.	Evaluable	EFF_T1	Summary of %Change in Fractional Excretion of Sucralose Values	Note: %CFB, Summary by: Study group and Visit, Page by: Timepoint	SAC		

10.8.6. Efficacy Figures

Efficacy	Efficacy: Figures						
No.	Population	IDSL / Example Shell	Title	Programming Notes	Deliverable [Priority]		
L/M ratio	L/M ratio						
2.1.	Evaluable	EFF_F1	Individual Plot of Absolute L/M Ratio Values Over Time for Healthy Subjects.	Y-axis: Absolute Values Plot by Timepoint	SAC		
2.2.	Evaluable	EFF_F2	Individual Plot of Absolute L/M Ratio Values Over Time for TI Subjects.	Y-axis: Absolute Values Plot by Timepoint Average value of Healthy Subjects will be used as reference line.	SAC		
2.3.	Evaluable	EFF_F2	Individual Plot of %Change L/M Ratio Values Over Time for TI Subjects.	Y-axis: %CFB Values Plot by Timepoint Average value of Healthy subjects will be used as reference.	SAC		
Fraction	al excretion of s	ucralose					
2.4.	Evaluable	EFF_F1	Individual Plot of Absolute Sucralose Values Over Time for Healthy Subjects.	Y axis: Absolute Values Plot by Timepoint	SAC		
2.5.	Evaluable	EFF_F2	Individual Plot of Absolute Sucralose Values Over Time for TI Subjects.	Y axis: Absolute Values, Plot by Timepoint Average value of Healthy subjects will be used as reference.	SAC		
2.6.	Evaluable	EFF_F2	Individual Plot of %Change Sucralose Values Over Time for TI Subjects.	Y axis: %CFB Values Plot by Timepoint Average value of Healthy subjects will be used as reference.	SAC		

L/M ratio	L/M ratio and Fractional excretion of sucralose					
2.7.	Evaluable	EFF_F3	Individual Plot of Absolue L/M ratio and Sucralose Values Over Time for TI Subjects.	Y axis: Absolute Values Plot by Timepoint Average values of Healthy subjects will be used as reference.	SAC	
2.8.	Evaluable	EFF_F3	Individual Plot of %Change L/M ratio and Sucralose Values Over Time for TI Subjects.	Y axis: %CFB Values Plot by Timepoint Average values of Healthy subjects will be used as reference.	SAC	

10.8.7. Safety Tables

Safety: Tables						
No.	Population	IDSL / Example Shell	Title	Programming Notes	Deliverable [Priority]	
Adverse	Adverse Events (AEs)					
3.1.	Safety	AE1CP	Summary of All Adverse Events by System Organ Class and Preferred Term	ICH E3 Include study group instead of treatment group.	SAC	
3.2.	Safety	AE15	Summary of Non-Serious Adverse Events by System Organ Class and Preferred Term (Number of Subjects and Occurrences)	FDAAA, EudraCT Include study group instead of treatment group.	SAC	
3.3.	Safety	AE1CP	Summary of Diseases Related Events by Verbatim Term		SAC	
Serious and Other Significant Adverse Events						
3.4.	Safety	AE16	Summary of Serious Adverse Events by System Organ Class and Preferred Term (Number of Subjects and Occurrences)	FDAAA, EudraCT	SAC	

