9.2. Adverse Events

9.2.1. Monitoring and reporting responsibilities

Healthy participants will be recruited to the HESTIA study alone and all AEs or SAEs occurring in this group should be managed according to this protocol.

Thermally injured participants recruited to this study will also be recruited to the SIFTI-2 study. The following guidance relates only to AEs or SAEs which the investigator reasonably believes to be the result of a procedure or requirement unique to this (the HESTIA) protocol. All other AEs or SAEs will be reported and managed in accordance with the SIFTI-2 protocol.

Unique procedures and requirements of HESTIA

1. The administration of STM
2. The collection of stool samples
3. Changes to standard of care for thermally injured participants:
 - a. The fasts required during the measurement of intestinal permeability
 - b. The use of alternative laxatives to lactulose and sennosides.

The definitions of an AE or SAE for this study can be found in [Appendix 4](#).

The investigator and any designees are responsible for detecting, documenting, and reporting events that meet the definition of an AE or SAE and remain responsible for following up AEs that are serious or that caused the participant to discontinue intestinal permeability measurement with the STM (see Section 8).

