10.5. Statistical Analyses

10.5.1. Safety Analyses

Administration of STM is for the measurement of intestinal permeability. The safety of this administration is not an endpoint of this study, but will be monitored and reported.

All safety data will be presented in data listings. Subject demographics, medical history, and prior and concomitant medications will be summarized using descriptive statistics. For continuous variables, these summaries will include number of subjects, mean, median, standard deviation, minimum, and maximum.

For categorical variables, the summaries will include frequencies and corresponding percentages. No inferential hypothesis testing will be performed on the safety variables.

Adverse events will be coded using the MedDRA classification system.

For healthy participants (who are recruited only to HESTIA), STM-emergent AEs will be defined as any AEs, regardless of relationship to STM administration, that occur after the first dose of STM until the final follow-up visit. The STM-emergent AEs will be summarized for the overall number of AEs and the percentage of subjects who experience them. The total number of AEs will be summarized overall. The AEs will be further summarized by severity and relationship to STM. If relationship information is missing, the AE will be considered STM-related. Listings for the subsets of SAEs and STM-related SAEs will be provided. The SAEs and number of AEs leading to discontinuation of STM administration will be summarized. The incidence of AEs will also be summarized by system organ class and preferred term.

For thermally-injured participants, STM-emergent AEs will be defined as any AE deemed related to STM administration that occurs after STM administration until the follow-up visit. The STM-related emergent AEs will be summarized for the overall number of AEs and the percentage of subjects who experience them. Listings for the subsets of SAEs and STM-related SAEs will be provided. The SAEs and number of AEs leading to discontinuation of STM administration will be summarized. The incidence of AEs will also be summarized by system organ class and preferred term.

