7.1. Adverse Events Analyses

Adverse events analyses including the analysis of adverse events (AEs), Serious (SAEs) and other significant AEs will be based on GSK Core Data Standards. The details of the planned displays are provided in Appendix 8: List of Data Displays.

NOTE: As detailed in Section 9.2.1 of the protocol, only AEs deemed to be related to procedures or requirements unique to the HESTIA study will be recorded/reported for thermally injured participants. All other AEs will be recorded/reported through the SIFTI-2 study.

Also, as given in Section 12.4 (Events NOT Meeting the AE Definition) in protocol, any clinically significant abnormal laboratory findings or other abnormal safety assessments which are associated with the underlying disease, unless judged by the investigator to be more severe than expected for the participant's condition will be considered as disease related event. Table 3 in protocol provides a list of commonly occurring AEs in participants with severe thermal injury which may meet this definition and will be entered as disease related events.

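### SAP adverse event tables place all-cause events in healthy participants beside HESTIA-related events only in burn patients, unlabelled, and the protocol's STM-related displays are not carried over

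*SAP*

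**What the plan says.** **Capture of events.** For healthy participants, protocol 9.2.1 states: "Healthy participants will be recruited to the HESTIA study alone and all AEs or SAEs occurring in this group should be managed according to this" (that is, under HESTIA). For thermally injured participants, SAP 7.1 repeats the protocol's restriction that "only AEs deemed to be related to procedures or requirements unique to the HESTIA study will be recorded/reported for thermally injured participants", and adds: "All other AEs will be recorded/reported through the SIFTI-2 study".

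**Protocol analysis (10.5.1).** In healthy participants, "STM-emergent AEs will be defined as any AEs, regardless of relationship to STM administration, that occur after the first dose of STM". In injured participants, "STM-emergent AEs will be defined as any AE deemed related to STM administration that occurs after STM administration until the follow-up visit". The healthy paragraph adds: "The AEs will be further summarized by severity and relationship to STM". The injured paragraph plans a summary of STM-related emergent events. Both paragraphs state: "Listings for the subsets of SAEs and STM-related SAEs will be provided".

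**SAP displays.** SAP 4.1 makes study group the column variable for tables and listings. SAP 10.8.7 lists four safety tables:

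- 3.1, "Summary of All Adverse Events by System Organ Class and Preferred Term"
- 3.2, non-serious events, tagged for FDAAA and EudraCT
- 3.3, disease-related events
- 3.4, serious events, also tagged for FDAAA and EudraCT

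The notes to 3.1 and 3.2 repeat the study-group instruction. Table 3.4 has no such note and falls under the general rule.

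**The concern.** A table with one title and two group columns invites the reader to compare the columns. Here they count different things. One holds everything that happened to a participant after the sugar test material. The other holds only what an investigator attributed to a HESTIA procedure. A lower figure in the injured column could be taken as better tolerability, or as a low event burden in burn patients, when it reflects where the event was recorded. Tables 3.2 and 3.4 are tagged for public disclosure, where the explanation in SAP 7.1 may not accompany them.

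The displays that would help with reading across groups are those restricted to STM-related events. The protocol asks for these in some form in each group, and the SAP names none of them.

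**Working it through.** The plan gives no figure to reproduce on this point. The check is a comparison of the two documents, followed by an illustration.

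**1. What each column of Table 3.1 contains**

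| | Healthy | Thermally injured |
|---|---|---|
| Events recorded in HESTIA | All (protocol 9.2.1) | Only those related to HESTIA-specific procedures (SAP 7.1; protocol 9.2.1 and Appendix 4) |
| Protocol 10.5.1 analysis set | Any event after first dose | STM-related events only |
| Events recorded elsewhere | None | All other events, in SIFTI-2 |
| Label or footnote specified | None | None |

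**2. Whether the injured column stands in for the protocol's STM-related summary.** It does not. Protocol 9.2.1 counts as HESTIA-specific not only STM administration but also stool collection, the test fasts and the change of laxative. The injured column is therefore wider than STM-related and narrower than all-cause.

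**3. Whether the protocol's displays reappear in the SAP**

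| Protocol 10.5.1 item | Named SAP display | Logged in SAP Table 1 |
|---|---|---|
| Severity and relationship summary (healthy) | None | No |
| STM-related event summary (injured) | None | No |
| STM-related serious event listing (both groups) | None | No |

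The AE and SAE listings in SAP 10.8.10 (Listings 13 to 19) were checked for the third row.

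**4. Illustration of the recording effect.** The only document input is the 3 injured participants (SAP 1.1; 25 were planned). The rest are assumptions that the documents do not give: the same true all-cause incidence p in both groups, and a fraction r of affected injured participants with a HESTIA-related event.

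- Expected healthy column: p
- Expected injured column: p × r
- Chance that the injured column is empty: (1 − p × r)³
- The same chance if all events were captured: (1 − p)³

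| p | r | Healthy | Injured | Chance of 0/3 as planned | Chance of 0/3 with full capture |
|---|---|---|---|---|---|
| 30% | 10% | 30% | 3% | 0.97³ = 91% | 0.70³ = 34% |
| 30% | 50% | 30% | 15% | 0.85³ = 61% | 34% |
| 60% | 10% | 60% | 6% | 0.94³ = 83% | 0.40³ = 6% |
| 60% | 50% | 60% | 30% | 0.70³ = 34% | 6% |
| 90% | 10% | 90% | 9% | 0.91³ = 75% | 0.10³ = 0.1% |
| 90% | 50% | 90% | 45% | 0.55³ = 17% | 0.1% |

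Over this range an empty injured column has a 17% to 91% chance, although the groups are identical by construction.

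**The case against.** The best defence is that the asymmetry is a protocol design choice, repeated openly in SAP 7.1, the section that governs these tables. Beside tables for non-serious and serious events, *all* can be read as all events recorded in HESTIA whatever their seriousness. Disease-related events have their own Table 3.3, and Listing 17 gives them for injured participants. The sponsor's standard shells are not in the documents, so relationship and severity may already appear in the listing of all events (Listing 13), which might suffice for 3 people.

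Most of this stands, and it limits the point to labelling and unlogged omissions. It does not remove it. A reader of the table does not have SAP 7.1 at hand, Table 3.3 does not make Table 3.1 all-cause for the injured group, and a possible column in an unseen shell is not a planned summary.

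Several stronger readings are tempting and are not supported:

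- *That all three tables claim to show all events.* Only Table 3.1 does.
- *That the tables will show fewer events in burn patients.* That depends on the data; healthy participants may report few or none.
- *That the SAP dropped a between-group relationship comparison.* The protocol places the severity and relationship summary in the healthy paragraph only and plans no by-group table.
- *That the plan fails to deliver a valid comparison of STM tolerability.* It never set out to: protocol 10.5.1 says STM safety is not an endpoint and plans no inferential safety testing.

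**Conclusion.** The point holds as a minor one. Tables 3.1, 3.2 and 3.4 put differently captured events side by side without saying so on the table, and the title of 3.1 is the most exposed. Three protocol displays have no named SAP counterpart and no entry in the table of changes.

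The distortion cannot be sized from the documents. The 17% to 91% range rests wholly on the assumed incidences and related fractions and shows only that the recording rule alone can empty the injured column. Practical weight is low: the study stopped early, reporting is descriptive, and no layout gives an informative group comparison with 3 injured participants. The finding on omissions assumes that the sponsor's standard shells, which the documents do not reproduce, contain no such summaries.

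**What to change.** 1. Label the injured-group columns of Tables 3.1, 3.2 and 3.4: *HESTIA-related AEs only; other AEs recorded in SIFTI-2; disease-related events in Table 3.3*.
2. Add one by-group table of STM-related events by severity. Base it on the single relationship-to-STM assessment that protocol Appendix 4 already requires for every event, together with the intensity grade, so that both columns use one definition. A table of events related to any HESTIA procedure is less safe, because the documents do not show that relatedness to the other procedures is recorded for healthy participants. State whether the protocol's rule that a missing relationship counts as STM-related, written for healthy participants, applies to both groups.
3. Add the listing of STM-related serious events.
4. Record any protocol 10.5.1 display still omitted in SAP Table 1, with the reason.

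Making Table 3.1 healthy-only is optional once the column is labelled.

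The cost is one small table, one listing and some label text, with no new data collection. The added output is purely descriptive.

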10.8.8. Biomarker Tables

Pharma	codynamic and	Biomarker: Tables			
No.	Population	IDSL / Example Shell	Title	Programming Notes	Deliverable [Priority]
Intestin	al Permeability				
4.1	Evaluable	PD_T1	Summary of Markers of Intestinal Mucosal Damage	Note: Absolute Values Summary by: Study group and Visit	SAC
4.2	Evaluable	PD_T1	Summary of Change in Markers of Intestinal Mucosal Damage	Note: CFB Values Summary by: Study group and Visit	SAC
4.3	Evaluable	PD_T1	Summary of % Change in Markers of Intestinal Mucosal Damage	Note: %CFB Values Summary by: Study group and Visit	SAC
Bacteria	al Translocation				
4.4	Evaluable	PD_T1	Summary of Bacterial Markers of Translocation	Note: Absolute value Summary by: Study group and Visit	SAC
4.5	Evaluable	PD_T1	Summary of Change in Bacterial Markers of Translocation	Note: CFB Values Summary by: Study group and Visit	SAC
4.6	Evaluable	PD_T1	Summary of % Change in Bacterial Markers of Translocation	Note: %CFB Values Summary by: Study group and Visit	SAC

10.8.9. Biomarker Figures

Biomar	ker: Figures				
No.	Population	IDSL / Example Shell	Title	Programming Notes	Deliverable [Priority]
Biomar	kers				
4.1	Evaluable	PD_F1	Individual Plot for Markers of Intestinal Mucosal Damage (Absolute Values) Over Time	Trellis plot – One panel for each biomarker with all TI subjects. Include reference line which is average value of Healthy subjects. Note: Y axis - Absolute Values	SAC
4.2	Evaluable	PD_F1	Individual Plot for Markers of Intestinal Mucosal Damage (% Change from baseline Values) Over Time	Trellis plot – One panel for each biomarker with all TI subjects. Include reference line at Zero. Note: Y axis - %CFB Values	SAC
4.3	Evaluable	PD_F1	Individual Plot for Bacterial Translocation Associated Biomarkers (Absolute Values) Over Time	Trellis plot – One panel for each biomarker with all TI subjects. Include reference line which is average value of Healthy subjects. Note: Y axis - Absolute Values	SAC
4.4	Evaluable	PD_F1	Individual Plot for Bacterial Translocation Associated Biomarkers (% Change from baseline Values) Over Time	Trellis plot – One panel for each biomarker with all TI subjects. Include reference line at Zero Note: Y axis - %CFB Values	SAC

10.8.10. ICH Listings

ICH: Lis	stings				
No.	Population	IDSL / Example Shell	Title	Programming Notes	Deliverable [Priority]
Subject	Disposition				
1.	Screened	ES7	Listing of Reasons for Screen Failure	Journal Guidelines	SAC
2.	Screened	ES2	Listing of Reasons for Study Withdrawal	ICH E3	SAC
3.	Screened	SD2	Listing of Reasons for STM Discontinuation	ICH E3 Mention study group instead of Treatment group.	SAC
4.	Screened	AG1	Listing of STM administration		SAC
Protoco	ol Deviations				
5.	Screened	DV2	Listing of Important Protocol Deviations	ICH E3 Mention study group instead of Treatment group.	SAC
6.	Screened	IE3	Listing of Subjects with Inclusion/Exclusion Criteria Deviations	ICH E3 Include study group instead of treatment group.	SAC

ICH: Li	stings				
No.	Population	IDSL / Example Shell	Title	Programming Notes	Deliverable [Priority]
Popula	tions Analysed				
7.	Screened	SP3	Listing of Subjects Excluded from Any Population	ICH E3 Mention Evaluable population instead of ITT and per protocol population and study group instead of Treatment group	SAC
Demog	raphic and Base	line Characteristics			
8.	Screened	DM2	Listing of Demographic Characteristics	ICH E3 Include study group instead of treatment group. Include Baux score, % surface area burnt and Body mass index.	SAC
9.	Screened	DM9	Listing of Race	ICH E3 Include study group instead of treatment group.	SAC
Conco	mitant Medicatio	ns and Medical Hist	tory		
10.	Screened	СМЗ	Listing of Concomitant Medications	IDSL Mention study group instead of Treatment group.	SAC
11.	Screened	SU3	Listing of Substance Use	Include study group instead of treatment group.	SAC
12.	Screened	SP1	Listing of Subjects Who Had Surgery/Procedure	IDSL Include study group instead of treatment group.	SAC
Advers	se Events				
13.	Screened	AE8	Listing of All Adverse Events	ICH E3 Mention study group instead of Treatment group.	SAC
14.	Screened	AE7	Listing of Subject Numbers for Individual Adverse Events	ICH E3 Include study group instead of treatment group.	SAC

ICH: Lis	stings				
No.	Population	IDSL / Example Shell	Title	Programming Notes	Deliverable [Priority]
15.	Screened	AE2	Listing of Relationship Between Adverse Event System Organ Classes, Preferred Terms, and Verbatim Text	IDSL	SAC
Serious	and Other Sign	ificant Adverse Eve	nts	,	l
16.	Screened	AE8	Listing of Fatal Serious Adverse Events	ICH E3 Mention study group instead of Treatment group.	SAC
17.	Screened	AE8	Listing of Disease Related Outcomes/Events.	Only for TI participants.	
18.	Screened	AE14	Listing of Reasons for Considering as a Serious Adverse Event	ICH E3 Mention study group instead of Treatment group.	SAC
19.	Screened	AE8	Listing of Adverse Events Leading to Withdrawal from Study / Permanent Discontinuation of Study Treatment	ICH E3 Mention study group instead of Treatment group.	SAC
All Lab	oratory				
20.	Screened	LB5	Listing of All Laboratory Data for all Subjects	ICH E3, Mention study group instead of Treatment group.	SAC
21.	Screened	LB14	Listing of Laboratory Data with Character Results for all Subjects	ICH E3, Mention study group instead of Treatment group.	SAC
22.	Screened	UR2A	Listing of Urinalysis Data for all Subjects	ICH E3, Include study group instead of treatment group.	SAC
Vital Si	gns				
23.	Screened	VS4	Listing of All Vital Signs Data for all Subjects	IDSL Include study group instead of treatment group.	SAC

10.8.11. Non-ICH Listings

Non-ICI	H: Listings				
No.	Population	IDSL / Example Shell	Title	Programming Notes	Deliverable [Priority]
Efficacy	1				
24.	Screened	EFF_L1	Listing of Lactulose, Mannitol, L/M Ratio and Sucralose Data	Note: Numeric Score, CFB & %CFB	SAC
Biomar	kers				
25.	Screened	PD_L1	Listing of Biomarker Data	Note: Include Character result, Numeric score, CFB & %CFB.	SAC
Time to	wound recove	ry			
26.	Screened	TW_L1	Listing of Time to Wound Recovery Data for All TI Subjects		SAC
Subject	Characteristic	S			
27.	Screened	SC1	Listing of Subject Characteristics		SAC

10.9. Appendix 9: Example Mock Shells for Data Displays

Example SP1

Protocol: 206243
Population: Screened

Page 1 of 1

Table 1.5
Summary of Study Populations

Population	Healthy Subject s (N=200)	TI Subjects (N=250)	Total (N=500)		
Screened	200 (100%)	250 (100%)	500 (100%)		
Safety	195 (98%)	245 (98%)	440 (88%)		
Evaluable	200 (100%)	250 (100%)	460 (92%)		

206243

Page 1 of n

Example EFF_T1
Protocol: 206243

Population: Evaluable

Timepoint: 0-5 hours/0-24 hours

 $\label{thm:continuous} Table~2.1 \\ Summary~of~Lactulose: Mannitol~(L/M)~ratio~/~Change~in~Lactulose: Mannitol~(L/M)~Ratio~\\ \\$

Study Group	N	Visit	n	Mean	SD	SE	Median	Min.	Max.
Healthy Subjects	200	Day 1 Day 8 Day 15 Average	200 190 186 186	91.6 92.4 92.6 92.2	11.32 9.83 10.87 10.33	0.80 0.71 0.80 0.75	90.0 90.0 89.0 90.0	68 70 72 70	140 122 125 140
TI Subjects	200	Day 1 Day 3 Day 28 6 months	200 190 195 186 195	91.6 92.4 92.1 92.6 92.1	11.32 9.83 10.80 10.87 10.80	0.80 0.71 0.77 0.80 0.77	90.0 90.0 89.0 89.0 89.0	68 70 72 69 72	140 122 120 125 120

Note: Day 1 is considered as baseline for both the study groups.

Programming note:

Include all study visits for TI Subjects.

Produce same table for %Change from baseline values.

Produce similar tables for parameter Fractional excretion of sucralose.

Produce table for both the timepoints by page.

206243

Example PD_T1
Protocol: 206243

Protocol: 206243 Page 1 of n
Population: Evaluable

Table 3.1
Summary of Intestinal Permeability/ Bacterial Translocation Associated Biomarkers

Biomarkers(Unit)	Study Group	N	Visit	n	Mean	SD	SE	Median	Min.	Max.
Claudin 3	Healthy Subjects	200	Day 1	200	91.6	11.32	0.80	90.0	68	140
	TI Subjects	200	Day 1 Day 3 Day 28 6 months	200 190 195 186 195	91.6 92.4 92.1 92.6 92.1	11.32 9.83 10.80 10.87 10.80	0.80 0.71 0.77 0.80 0.77	90.0 90.0 89.0 89.0	68 70 72 69 72	140 122 120 125 120
Citrulline	Healthy Subjects TI Subjects	200	Day 1 Day 1 Day 3 Day 28 6 months	200 200 190 195 186 195	91.6 91.6 92.4 92.1 92.6 92.1	11.32 11.32 9.83 10.80 10.87 10.80	0.80 0.80 0.71 0.77 0.80 0.77	90.0 90.0 90.0 89.0 89.0	68 68 70 72 69 72	140 140 122 120 125 120

Note: Day 1 is considered as baseline for both the study groups.

Programming note:

Include all study visits for TI Subjects.

Produce same table for absolute, Change from baseline and % Change from baseline values for all biomarkers.

Page 1 of x

Example: EFF_L1
Protocol: 206243

Population: Screened

Study Group: Healthy Subjects

